## SUMMARY

In esophagogastric surgery, the appearance of a leak at the level of the anastomosis is the most feared complication with important repercussions for both the patient and his disease. There are many risk factors that are related to its appearance and that makes it difficult to prevent its appearance. Making an early diagnosis of it is important for optimal management and resolution and therefore, different studies have investigated the usefulness of the use of markers, both pre and postoperative, to predict possible postoperative complications such as anastomotic leak. Due to the importance of early diagnosis and management of possible complications after esophagogastric surgery, it is mandatory to research and create predictive models that identify patients with a high risk of suffering complications, in order to be able to act accordingly. indicating the complementary examinations that are considered adequate to obtain an early diagnosis.

The PROFUGO study (PRedictive Model for the Early Diagnosis of Anastomotic LEAK after esophagectomy and gastrectomy) is proposed as a prospective and multicenter study at the national level that aims to develop, with the help of artificial intelligence methods, a tool and predictive model that allows identifying cases with a high risk of anastomotic leak and/or major complications through the analysis of different clinical and analytical variables collected during the postoperative period of patients undergoing esophagectomy or gastrectomy.

## INTRODUCTION

Esophageal cancer is the sixth leading cause of cancer death worldwide, with an incidence that has been increasing in recent years. Surgery is the mainstay of curative therapy for fit patients with the ability to tolerate extensive surgical procedures. Postoperative morbidity associated with esophagectomy is high (around 60%) (1), pulmonary complications occur in 20-50% of patients, and anastomotic leak (AF) has a variable incidence depending on the series (0- 34%) (1, 2) with an associated mortality of 5-36% (3). Regarding gastric cancer, it represents the fifth most common and the second most frequent cause of death from cancer worldwide, with a rate of postoperative complications close to 40-50% (4).

Among the postoperative complications, AF is the most feared, presenting a high mortality rate. This complication is not only associated with a longer hospital stay and increased costs, but also with a worse prognosis of the disease and the patient's quality of life (5). The variability in the rate of AF in the literature is due to the lack of a precise definition that is generally accepted by all groups, as well as the need to establish a reliable and unanimous diagnostic method. In addition to possible technical failures, there are many potential risk factors that may be related to the appearance of this complication. Thus, patients with this type of pathology and due to factors such as accelerated metabolism and decreased intake present a high risk of malnutrition, hypoproteinemia and systemic inflammation, which can alter collagen synthesis, reduce tensile strength in the anastomosis, facilitate poor tissue healing and induce anastomotic dehiscence.

The diagnosis of AF, as well as that of other complications, is often made when the patient is symptomatic, requiring immediate and perhaps more aggressive intervention than if an earlier diagnosis had been made. Treatment is generally decided based on the size of the leak, the degree of local contamination, and the associated severity status of the patient. Thus, early diagnosis of AF by clinical, radiological and/or endoscopy is essential to provide immediate treatment through antibiotic therapy, placement of a feeding tube, application of endoscopic therapies, percutaneous drainage of collections, etc., possibly reducing the rate surgical review. For all these reasons, early prediction, diagnosis and treatment of possible major complications (Clavien-Dindo greater than 3), especially AF, are essential to improve the results and prognosis of the disease (6).

Different studies have investigated the usefulness of the use of markers, both pre and postoperative, to predict possible postoperative complications. Recent studies have evaluated different markers in early postoperative stages as predictors of AF and other major complications. These include C-reactive protein (CRP) (7), white blood cell count (RGB) (8), serum albumin (9), tumor necrosis factor  $\alpha$  (TNF  $\alpha$ ), interleukins 1 and 6, the CRP- albumin (CAR) (10-13), modified Glasgow Prognostic Score (mGPS), platelet/lymphocyte ratio and neutrophil/lymphocyte ratio (4) among others.

After carrying out a thorough bibliographic search, the small number of quality prospective studies in this area has been observed, most of them being retrospective or systematic reviews of retrospective studies.

CRP is one of the most studied inflammatory markers related to AF. It is mainly synthesized in the liver in response to proinflammatory cytokines, as an acute phase response protein, and its levels correlate with the severity of inflammation (14). CRP levels increase after surgery and commonly peak after 48 hours (15,16), subsequently decreasing in patients with an uncomplicated postoperative course. Therefore, CRP is especially valuable as a negative test, and a normal or falling CRP level on the third and fifth postoperative days (POD) can help predict which patients are not likely to develop AF (17). Although several prospective

studies and meta-analyses have shown that CRP is a useful marker of AF after colorectal surgery, the role of this marker in esophagogastric surgery is less well studied and established (18). In the study carried out by Aiolfi et al (19) it is concluded that postoperative CRP values can be useful to rule out rather than diagnose AF after elective esophagectomy. Thus, in the context of an enhanced recovery protocol, CRP could be used for early initiation and progression of oral diet and safe hospital discharge.

Liesenfeld et al (20) in a retrospective study of 233 patients, observed a less marked decrease in RGB after the 2nd POD in patients with AF, in addition to optimal diagnostic accuracy on the fourth postoperative day with a cut-off value of 8/ nl, which is within the normal RGB range. It was also found that CRP is an accurate negative predictive marker: for CRP levels below 155 mg/l from the 3rd to the 7th DPO, the negative predictive value for the absence of a leak was greater than 80%. The best precision for CRP was on the 4th DPO, with a cut-off value of 145 mg/l.

Serum albumin has been used as a simple nutritional marker to predict postoperative complications in various gastrointestinal surgeries (21).

In 2011, Noble and Underwood (22) developed the NUn score, through a retrospective study of 258 patients, calculated from the individual values of CRP, RGB and albumin on the 4th POD in patients who underwent esophagogastric resection with esophageal anastomosis. This score has a sensitivity greater than 95% when its value is greater than 10 and a specificity of 49%, as well as a high diagnostic precision for AF, which allows predicting, according to its values, the risk of appearance in asymptomatic patients, allowing personalized investigation and early intervention to prevent the development of significant morbidity and mortality. The NUn score was compared with other markers such as albumin, CRP, and RGB, and showed greater diagnostic accuracy, sensitivity, specificity, and statistical significance in predicting AF. In the retrospective study carried out by Brunded et al (23) of 382 patients, it was found that the NUn score is the best predictor of major complications, even greater than the CRP evaluated individually in patients undergoing esophagectomy.

Peritoneal levels of IL-6 and TNF $\alpha$  were significantly higher in patients with colorectal anastomosis leak compared to patients without leak in some studies and may contribute to their early detection (18), having found that increased levels Serum IL-6 is a predictor of AF in gastrointestinal surgery (24).

In the retrospective study of 330 patients carried out by Yansen et al (25), the neutrophil-lymphocyte ratio (NLR) was used as a biochemical marker. The incidence of AF was 16%, 47.2% of them being treated by surgery. An increasing trend in RLN was significantly associated with the need for surgical intervention, with the mean leak diagnosis time being 7 days and 49.1% being grade III AF. An NLR cut-off value of 10 at the 3rd POD had 74.5% sensitivity, 58% specificity, 25% positive predictive value, and a value of less than 10 had 92.4% negative predictive value for leaks. The results of this study concluded that the value of NLR is more relevant in its negative predictive values and helps in making postoperative decisions with more confidence. On the contrary, an increasing trend of RLN between 1st and 3rd DPO is an independent factor of AF that should be alerted to its suspicion.

Findlay et al (26) developed a prospective study of 326 patients where it was concluded that the use of elevated inflammatory markers is more useful in diagnosis than in prediction, therefore, these parameters do not seem to be very useful for diagnosis and management. early AF. Similar conclusions were obtained in the work published by Liesenfeld et al (20) where the CRP, RGB and NU scores are not recommended as independent markers for the prediction of AF after transthoracic esophageal resection. Another retrospective study by Sugimoto et al (13) of 295 patients analyzed preparatory inflammatory and nutritional markers and studied their relationship with the appearance of postoperative AF in esophageal cancer. The study compared the predictive capacity of preoperative CAR, nutritional prognostic index (PNI), and mGPS for AF, and identified that an elevated value of preoperative CAR ( $\geq 0.0139$ ), but not PNI or mGPS, is a useful indicator for predict the occurrence of AF after esophagectomy. The results of their study suggest that preoperative CAR is a promising predictive marker of AF.

For all these reasons, the evidence on the usefulness of different markers for early prediction of AF and/or major complications after esophagogastric resection surgery is still limited, and quality prospective studies with an adequate sample size are needed to be able to draw more accurate conclusions. .

On the other hand, due to the importance of early diagnosis and management of possible complications after esophagogastric surgery, it is mandatory to research and create predictive models that identify patients with a high risk of suffering complications, in order to be able to Act accordingly, indicating the complementary examinations that are considered appropriate to obtain an early diagnosis, thus avoiding further deterioration of the patient and a possible septic situation in more advanced states. For this purpose, this study has been designed to try to create a predictive model that allows identifying patients with a high risk of anastomotic leak and/or major complication during the postoperative period of esophagogastric tumor resection surgery, through the analysis of different clinical variables and analytics collected in the postoperative period.

## **HYPOTHESIS**

The appearance of AF in esophagogastric surgery is one of the most serious complications and marks the postoperative course and prognosis of the disease. One of the most important pillars in the management of AF is its early diagnosis, there is a gap in the literature on the role of inflammatory biomarkers in its prediction and an urgent need to identify and develop predictive tools for this purpose.

Thus, the early identification of patients at high risk of the appearance of AF and/or major complications after esophagogastric surgery through the daily postoperative study of objective clinical variables and analytical markers would allow an earlier diagnosis and more appropriate treatment of said situation, thus avoiding a greater deterioration of the patient and a possible septic situation in more advanced states that compromise their clinical evolution and the prognosis of their disease.

## OBJECTIVES

Based on the hypothesis of the study, the main and secondary objectives of this study are established:

- Main goal:

\*Design a predictive model based on clinical and analytical variables that allow identifying patients with a high risk of anastomotic leak (main variable) during the postoperative period of esophagogastric surgery.

- Secondary objectives:

\* Design a predictive model based on clinical and analytical variables that allow identifying patients at high risk of other major complications (Clavien-Dindo greater than 3) during the postoperative period of esophagogastric surgery.

\* Individually describe the postoperative evolution of the clinical and analytical parameters studied in patients without major complications or AF and those who did suffer from any of them.

\* Describe the complications and types of AF diagnosed in the study.

\* Assess the day AF was diagnosed and the treatment used for its possible resolution.

\* Assess the day AF was diagnosed and hospital stay.

\* Compare the preoperative Glasgow prognostic score (mGPS) and the biochemical value of inflammatory markers (CRP, Interleukin 6 (IL-6) and procalcitonin) and the appearance of AF.

\* Assess the AF resolution capacity of each technique used.

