## **8.2.- PARTS of the DATABASE**

After opening the REDCAP application of the AEC, you can access the data set and the different variables to be collected at each moment of the care process and which will be described in more detail below:

The main outcome variable of the study is ANASTOMOTIC LEAKAGE, a categorical variable divided into the following categories, according to the consensus definitions of the Consensus Group on Complications of Esophagectomy (ECCG) (27), which in this study will be applicable both to fistulas occurred after esophagectomy and after gastrectomy:

- NO: If this complication did not occur.
- I: Defect that does not require specific treatment or that can be treated medically or with diet modification
- II: Defect that requires some intervention, but not surgical, such as: drainage by interventional radiology, prosthesis placement, opening of the wound at the bedside, compression or wound healing.
- III: Defect requiring surgical intervention

In relation to this variable, the following data are also included in the study:

- DAY Dx LEAK (DAY of DIAGNOSIS OF THE ANASTOMOTIC LEAK: ordinal variable that shows the number of the postoperative day on which the diagnosis of the anastomotic leak occurred.
- EDA Dx LEAK (LEAK DIAGNOSIS THROUGH ENDOSCOPY): Dichotomous variable: YES/NO.
- CAT Dx LEAK (DIAGNOSIS OF LEAK BY CAT): Dichotomous variable: YES/NO.

The rest of the variables collected in this study are:

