### **8.2.3.- RESULTS**

- ORAL TOLERANCE BEGINNING DAY: postoperative day number on which the patient begins to tolerate food and/or water orally. Continuous variable expressed in days.
- DISCHARGE DATE (DATE OF INTERVENTION): in day/month/year format

- CLAVIEN DINDO COMPLICATION (CLASSIFICATION OF POSTOPERATIVE COMPLICATIONS ACCORDING TO CLAVIEN-DINDO): Categorical variable divided into the following categories:

- NO COMPLICATION: If this complication did not occur.
- I: Any deviation from the normal postoperative course WITHOUT the need for pharmacological treatment or surgical, endoscopic and radiological interventions Acceptable therapeutic regimens are drugs such as antiemetics, antipyretics, analgesics, diuretics and electrolytes and physiotherapy. This grade also includes open wound infections at the patient's bedside.
- II: Requires pharmacological treatment with medications other than those authorized for grade I complications. Blood transfusions and total parenteral nutrition are also included.
- IIIa: Requires surgical, endoscopic or radiological intervention with local anesthesia.
- IIIb: Requires surgical, endoscopic or radiological intervention under general anesthesia.
- IVa: Life-threatening complication (including central nervous system complications: cerebral haemorrhage, cerebral infarction, subarachnoid haemorrhage, but excluding transient ischemic attacks) requiring Intermediate/Intensive Care Unit management. Single organ dysfunction (includes dialysis)
- IVb: Life-threatening complication (including central nervous system complications: cerebral haemorrhage, cerebral infarction, subarachnoid haemorrhage, but excluding transient ischemic attacks) requiring Intermediate/Intensive Care Unit management. Multi-organ dysfunction.
- V: Death of the patient.

- NECROSIS of the PLASTY: Categorical variable divided into the following categories according to the consensus definitions of the Consensus Group on Complications of Esophagectomy (ECCG) (27):

- NO: If this complication did not occur.
- I: Focal necrosis of the graft identified endoscopically, which does NOT require surgical treatment.
- II: Focal necrosis of the graft identified endoscopically, requiring surgical treatment, but not esophageal diversion
- III: Extensive necrosis of the graft, which requires surgical treatment with resection of the graft and esophageal diversion.

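### The cut-off for a major complication, a Clavien-Dindo grade above 3, as written leaves out grades IIIa and IIIb; the protocol should list the grades that count

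*Combined protocol and SAP*

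**What the plan says.** The combined protocol and SAP attaches a grade to the term 'major complication' in two places, with the same cut-off in both. The first secondary objective (OBJECTIVES) is a model "identifying patients at high risk of other major complications (Clavien-Dindo greater than 3) during the postoperative period of esophagogastric surgery". The INTRODUCTION argues for early detection of "possible major complications (Clavien-Dindo greater than 3), especially AF", where AF stands for anastomotic leak.

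The recorded variable (section 8.2.3, RESULTS) has no undivided grade 3. Its third level is split. The lower half reads "IIIa: Requires surgical, endoscopic or radiological intervention with local anesthesia". The upper half differs only in the kind of anaesthesia and reads "IIIb: Requires surgical, endoscopic or radiological intervention under general anesthesia".

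Above these come IVa and IVb (life-threatening, with single-organ or multi-organ dysfunction) and V (death). The section does not say which grades count as major.

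The main outcome, anastomotic leak, has its own scale in section 8.2 (PARTS of the DATABASE):

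- The mildest of the three leak types is worded as "I: Defect that does not require specific treatment or that can be treated medically or with diet modification".
- The middle type, which covers procedures short of an operation, is worded as "II: Defect that requires some intervention, but not surgical, such as: drainage by interventional radiology, prosthesis placement, opening of the wound at the bedside"; its list of examples then goes on to compression and wound care.
- The most severe type is worded as "III: Defect requiring surgical intervention".

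The sample-size section assumes that about 30% of patients have a major complication, leak included, and gives no grade. The data analysis section uses major complications as an outcome of the univariate screen, also without a grade.

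**The concern.** An outcome threshold must tell the analyst which recorded categories are events. This one does so only if it is taken at its word, and the result is unexpected. Patients who needed a surgical, endoscopic or radiological intervention, including under general anaesthesia, are coded as having had no major complication.

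Three uses of the outcome are affected:

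- the dependent variable of the secondary prediction model, and so the major-complication output of the planned application;
- the univariate screen at p < 0.1 for major complications;
- the descriptive comparison of patients who had neither a major complication nor a leak with those who had either one.

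In the third use, a patient with no leak who was reoperated under general anaesthesia would sit in the reference group, and the contrast in postoperative markers could be diluted. If the authors had grade III or higher in mind, two analysts could code the outcome differently from the same protocol. A choice left until the data are visible could also be influenced by how each model performs.

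**Working it through.** The point is one of definition, so the check is mainly to set the sections side by side.

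1. **Grades kept under each reading** (cut-off from OBJECTIVES and INTRODUCTION, grades from section 8.2.3):

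| Recorded grade | Above 3, literal | III or higher |
|---|---|---|
| I, II | no | no |
| IIIa, IIIb | no | yes |
| IVa, IVb | yes | yes |
| V | yes | yes |

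From IIIa upward there are 5 recorded grades. The literal rule keeps 3 and drops 5 − 3 = 2. The two readings differ by exactly the patients recorded as IIIa or IIIb.

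2. **Does another section settle it?** The summary, hypothesis, design, sample-size, data analysis and application text all use the term without a grade. None corrects or confirms the cut-off.

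3. **Fit with the Introduction.** The Introduction singles out leak among major complications. Leak type III requires surgery. Two of the type II examples, drainage by interventional radiology and prosthesis placement, are also procedures of the kind that define Clavien IIIa and IIIb. The other type II examples do not clearly match. Bedside wound opening in particular resembles the wording of Clavien grade I: "This grade also includes open wound infections at the patient's bedside". Under the literal rule, a leak treated by surgery, drainage or prosthesis is therefore not a major complication through its treatment alone. It becomes one only if the patient's recorded grade is IV or V.

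4. **Does the 30% identify the reading?** The sample-size section gives 847 patients for a proportion of 30%, precision 3% and 95% confidence. The usual formula gives n = 1.96² × 0.30 × 0.70 / 0.03² ≈ 896.3, so 897 and not 847. That gap is a separate matter and is not evidence for either reading. The 30% includes leak and has no grade attached, so it cannot show whether IIIa and IIIb were counted.

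5. **Size.** The documents give no distribution of Clavien grades, so the number of patients affected cannot be derived. For scale only, suppose a share s of 847 patients is recorded as IIIa or IIIb. The number that changes status is 847 × s:

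- s = 5%: about 42
- s = 10%: about 85
- s = 15%: about 127

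These shares are assumptions and not estimates from the protocol.

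**The case against.** The strongest reply is that the rule is clear. A grade above 3 maps onto IVa, IVb and V, the same wording appears twice, and no section states a different threshold. If the authors want only life-threatening events and death, that is a legitimate choice of outcome. If they wrote loosely and will code III or higher, nobody is misclassified. Harm arises only if III was intended and the analyst follows the text.

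Much of this stands. A reader might infer that the cut-off cannot be applied to the recorded grades, but it can. A reader might also infer that the protocol contradicts itself, but some leaks reach grade IV or V, so the literal rule and the Introduction can both hold. Nor do the documents show that III or higher was meant. The English appears to be a translation, and section 4.1.2 of the task distribution lists separate instructions with variable definitions that are not among the text reviewed here. Either could explain the wording, and neither settles it.

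Two supporting arguments should not be used. One is that most type II leaks correspond to Clavien III; only the drainage and prosthesis examples clearly do. The other is to count the complication categories that are defined by a procedure and report that the literal rule captures none of them. That result follows from how the categories were chosen and says nothing about patients.

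The reply does not remove the problem in the text. Section 4.3 gives the modelling to a data analysis laboratory in an engineering department, which may reasonably code what is written.

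**Conclusion.** The concern holds in a limited form. As written, the threshold makes every patient recorded as IIIa or IIIb a non-event for major complications. That sits poorly with the Introduction's emphasis on leak, and no visible section corrects it. It should be settled before the outcome is coded.

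The conclusion assumes that the cut-off is applied as written to the single Clavien variable in section 8.2.3. That section does not say whether the variable holds each patient's highest grade.

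A reader might infer that a large group of patients is miscoded or that the main result is at risk. The documents support neither inference. They give no grade frequencies, and the primary model predicts leak from its own scale, which does not use the Clavien cut-off.

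**What to change.** Before analysis, replace the bracketed cut-off in the INTRODUCTION and OBJECTIVES with an explicit list, in one of two forms:

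- Clavien-Dindo grade IIIa or higher (IIIa, IIIb, IVa, IVb, V); or
- if only the upper grades are truly meant, grades IVa, IVb and V, with the Introduction's sentence on leak reconciled to that choice.

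In the sample-size section, state which definition the 30% refers to. Repeat the list, or refer to it, in the data analysis section.

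The cost is a few words of protocol text. Every grade is already recorded, so the choice of cut-off changes no data collection.

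A secondary clarification could be made at the same time. The objective speaks of other major complications, whereas the sample-size section includes leak. One sentence should say whether leak patients are events, non-events or excluded in the second model. If they are to be coded by their non-leak complications, check first that a single Clavien variable can show which complication produced the grade.

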### 4.- Sample size

The purpose of the study is to recruit as many patients as possible from all national centers who wish to participate.

For an alpha error of 5% (95% confidence) with a precision of 3% and estimating a number of patients with major complications (including AF) around 30%, the calculation of the sample size yields a total of 847 patients. However, the final sample size may be smaller depending on the proportion of complications detected and the statistical and artificial intelligence models to create the predictive model will be adapted to the event rate provided by the recruited sample.

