- DIA Dx NECROSIS (DAY OF DIAGNOSIS OF PLASTY NECROSIS): ordinal variable that shows the number of the postoperative day on which the diagnosis of plasty necrosis occurred

- EDA Dx NECROSIS (DIAGNOSIS OF PLASTY NECROSIS BY ENDOSCOPY): Dichotomous variable: YES/NO.

- CAT Dx LEAK (DIAGNOSIS OF PLASTY NECROSIS BY CAT): Dichotomous variable: YES/NO.

- CHYLOTHORAX: Categorical variable divided into the following categories according to the consensus definitions of the Consensus Group on Complications of Esophagectomy (ECCG) (27):

- NO: If this complication did not occur.
- Ia: Debit less than 1 liter per day - Treatment: changes in the enteral diet
- Ib: Debt greater than 1 liter per day - Treatment: changes in the enteral diet
- IIa: Debt less than 1 liter per day – Treatment: total parenteral nutrition
- IIb: Debt greater than 1 liter per day – Treatment: total parenteral nutrition
- IIIa: Debit less than 1 liter per day - Treatment: interventional radiology or surgery
- IIIb: Debt greater than 1 liter per day - Treatment: interventional radiology or surgery

- DAY Dx CHYLOTHORAX (DAY of DIAGNOSIS OF CHYLOTHORAX): ordinal variable that shows the number of postoperative day on which the diagnosis of chylothorax occurred.

- RECURRENT INJURY: Categorical variable divided into the following categories according to the consensus definitions of the Esophagectomy Complications Consensus Group (ECCG) (27):

- NO: If this complication did not occur.
- Ia: Transient unilateral lesion that does NOT require treatment (dietary modifications allowed)

- Ib: Transient bilateral lesion that does NOT require treatment (dietary modifications allowed)
- IIa: Unilateral injury that requires scheduled and deferred surgical treatment (such as thyroplasty or medialization procedure)
- IIb: Bilateral lesion that requires scheduled and deferred surgical treatment (such as thyroplasty or medialization procedure)
- IIIa: Unilateral lesion requiring urgent or preferential surgical treatment due to episodes of aspiration or respiratory problems (such as thyroplasty or medialization procedure)
- IIIb: Bilateral lesion requiring urgent or preferential surgical treatment due to episodes of aspiration or respiratory problems (such as thyroplasty or medialization procedure)
  
- DAY Dx RECURRENT INJURY (DAY of DIAGNOSIS OF THE RECURRENT NERVE INJURY): ordinal variable that shows the postoperative day number on which the diagnosis of the recurrent nerve injury occurred.
  

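### The Clavien-Dindo grade has no cause and no day, so the secondary model of other major complications mixes in leak-driven grades to an unknown degree and can only partly be timed against the markers

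*Combined protocol and SAP*

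**What the plan says.** The main objective is a model for anastomotic leak. The first secondary objective is a second model, for "identifying patients at high risk of other major complications (Clavien-Dindo greater than 3) during the postoperative period of esophagogastric surgery" (OBJECTIVES).

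The severity information for that second model is one entry in section 8.2.3: "CLAVIEN DINDO COMPLICATION (CLASSIFICATION OF POSTOPERATIVE COMPLICATIONS ACCORDING TO CLAVIEN-DINDO): Categorical variable divided into the following categories", running from no complication to grade V. No linked field gives the cause or the day.

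Leak is a separate variable in section 8.2, with its own grade and a day of diagnosis: "ordinal variable that shows the number of the postoperative day on which the diagnosis of the anastomotic leak occurred". Leak grade II is described as "II: Defect that requires some intervention, but not surgical, such as: drainage by interventional radiology, prosthesis placement" among other measures, and the top grade as "III: Defect requiring surgical intervention".

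Section 4 (Sample size) works from "estimating a number of patients with major complications (including AF) around 30" per cent, where AF is the plan's abbreviation for leak. The summary, the end of the introduction and the design section refer to leak and/or major complications. The data analysis section relates the study variables to leak and to major complications. It says nothing about how the two outcomes overlap, or about keeping outcome events later than the markers.

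**The concern.** A model of complications other than leak needs an outcome from which leak can be removed. It also needs an event day, because the markers are taken on postoperative days 1, 2, 3, 4 and 6 and the tool is meant to warn before the event.

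A single grade with no cause and no day supplies neither directly. A leak treated by surgery, or by radiological or endoscopic intervention, meets the plan's own description of Clavien-Dindo III. Such patients can therefore be events in both models. The second model could then seem to predict non-leak complications while part of its signal is leak. Marker values taken after an early major event could also be used to predict that same event. The plan is inconsistent on whether leak belongs in the outcome: OBJECTIVES says other complications, and Sample size says leak is included.

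**Working it through.** **1. What can be attributed and dated**

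| Item (sections 8.2 and 8.2.3) | Severity recorded | Day recorded |
|---|---|---|
| Clavien-Dindo grade | yes, cause not linked | no |
| Leak | own grade | yes |
| Plasty necrosis, chylothorax, recurrent nerve injury | own grade | yes |
| Atrial fibrillation, respiratory infection, surgical site infection, wound infection | yes/no only | yes |
| Death | cause category | yes |
| Readmission | free-text cause | yes |
| Other non-fatal in-hospital events (e.g. bleeding, infarction, renal failure, non-leak reoperation) | no variable of their own | no |

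Four situations follow.
- Leak absent: the grade is non-leak by construction.
- Leak present with a second complication, for example respiratory infection and grade IVa: the grade cannot be assigned to either.
- Several complications, for example atrial fibrillation on day 2, respiratory infection on day 8 and grade IVa: both days are known, but not which one dates the grade.
- Unlisted in-hospital event: neither cause nor day is available, so day 3 to 6 markers cannot be shown to precede it.

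**2. The plan's own figure**

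Section 4 gives 847 patients for 30% ± 3% at 95% confidence. The usual formula gives n = 1.96² × 0.30 × 0.70 / 0.03² ≈ 896.3, so 897. The stated 847 does not reproduce. That is a separate matter; 847 is used below only to turn shares into counts. Expected major events: 0.30 × 847 = 254.

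**3. How much of the outcome could be leak**

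Share = leak rate × fraction of leaks that are major / 0.30.

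The 30% is from section 4. The 16% leak rate is from one cited retrospective series in the introduction. The other leak rates and all the fractions except 47.2% are assumptions.

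| Leak rate | Fraction major | Share of major events | Leak-driven | Remaining |
|---|---|---|---|---|
| 5% | 50% | 0.025/0.30 = 8% | 21 | 233 |
| 10% | 50% | 0.05/0.30 = 17% | 42 | 212 |
| 10% | 100% | 0.10/0.30 = 33% | 85 | 169 |
| 16% | 50% | 0.08/0.30 = 27% | 68 | 186 |
| 16% | 100% | 0.16/0.30 = 53% | 136 | 119 |
| 25% | 100% | 0.25/0.30 = 83% | 212 | 42 |

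The remaining column assumes that no leak patient had a separate major event.

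One partly document-based check is possible if grade III counts as major. The same series reports 47.2% of leaks treated surgically, and surgery is at least Clavien-Dindo III. So 0.16 × 0.472 / 0.30 = 0.0755 / 0.30 = 25%, before any leak treated endoscopically or radiologically is added.

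The share reaches one half only when leak rate × fraction major is at least 0.15.

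**4. Dependence on the cut-off**

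The objective sets the threshold as greater than 3. Read literally, that is grades IV and V. A leak drained, stented or reoperated without organ failure would then fall outside it, and the shares above would not apply. Section 4 ties its 30% to no grade.

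**The case against.** Leak is its own graded and dated variable, so leak-free patients can be modelled separately with no new field. Seven other complications and death are dated, and readmission has a day and a cause. Necrosis, chylothorax and nerve injury carry treatment-based grades. The wording elsewhere in the plan (leak and/or major complications) suggests that an overlapping endpoint was intended and that *other* is loose drafting. Section 8.2.3 does not say whether the Clavien-Dindo entry is the worst grade or is repeated per complication, and the REDCap form is not shown.

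Most of this stands, and it rules out three stronger readings that a reader might infer.
- That the second model largely re-predicts leak. This rests on assumed rates. The share passes one half only at the upper end, the 16% is one series' rate applied to a mixed esophagectomy and gastrectomy cohort, and the cut-off is unsettled. Nor does every leak with "Defect that requires some intervention, but not surgical" reach Clavien-Dindo III: leak grade II also covers bedside wound opening, and Clavien-Dindo I takes in wound infections handled that way.
- That outcome events cannot be ordered against the markers at all, or that the objective is unanswerable. Timing and separation are partly recoverable from the fields above.
- That unlisted events leave a trace only if fatal. Those leading to readmission have a day and a cause.

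The objection does not remove the remaining gap. Restricting to leak-free patients discards true non-leak events in leak patients and conditions on something not yet known when the tool would be used. The separate complication days do not date the grade. If the overlap is intended, the objective still contradicts section 4.

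**Conclusion.** The point holds in a limited form. The secondary outcome is not uniquely defined, and the grade that defines it cannot be attributed in a leak patient with a second complication. It cannot be placed before or after the day 1 to 6 markers when the event is unlisted and in-hospital, or when several or ungraded complications coexist. For those patients the information is not collected, so an analysis rule alone would not recover it.

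The leak contribution is unknown and possibly substantial. It runs from 8% to 83% of major events over assumed leak rates of 5–25% with half to all leaks major, and is 27–53% at the cited 16%. These figures rest on the 30% event rate and on counting grade III as major; they are not estimates for this cohort.

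The conclusion takes the Clavien-Dindo entry as one value per patient, which is how section 8.2.3 reads but is not stated there. The primary leak model is not affected. For a secondary objective with a cheap remedy, the change should be made.

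**What to change.** In section 8.2.3 add three fields for the highest-grade complication other than leak: its Clavien-Dindo grade, its cause from a short list, and its postoperative day. In OBJECTIVES and the data analysis section, define the secondary outcome as a major complication not attributable to leak and occurring after the marker day used. State whether grade III counts as major.

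If fields cannot be added for patients already entered:
- model the composite of leak or major complication;
- drop *other* from the objective, and bring OBJECTIVES and section 4 into line;
- report a sensitivity analysis in patients without leak;
- state that event timing is incomplete.

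The cost is a little more data entry, from records the sites already review over the 90-day follow-up, and a few sentences of text. The statistical cost is fewer events for the secondary model. On the illustrative figures, 254 would fall to 212 (10% leak, half major) or 119 (16% leak, all major), less any reduction offset by leak patients who also had a separate major complication.
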